#### **10.1.2 Missing Data**

If any information is not available, and it is considered by the investigator that it will never be available (e.g. the weight on a particular visit was not recorded), the investigator will explain in the eCRF, why the investigation was missed out (e.g. the patient was not well enough to undergo the procedure).

#### **10.1.3 Storage**

It will be the responsibility of the investigator to guarantee adequate storage for all study records, including the hospital notes during the study (and for a minimum of 25 years following the end of the study). If he/she leaves the employ of the hospital he/she will inform the sponsor and nominate a contact person who will have access to the study documents.

The investigator should take measures to prevent accidental or premature destruction of these documents. Essential documents shall be stored in such a way that ensures that they are readily available upon authorities' request.

Archiving is described in Section [10.6](#).

## 10.2 Monitoring

This study will be monitored at all stages of its development by the clinical research personnel designated by the sponsor. Monitoring will include personal visits and telephone communication to ensure that the investigation is conducted according to the protocol and in order to comply with guidelines of GCP and applicable regulatory requirements. On-site and remote (according to local regulations) review of CRFs will include a review of forms for completeness and clarity, and consistency with source documents available for each patient.

During monitoring visits, the data recorded in the CRFs, source documents, and other study-related records will be compared against each other in order to ensure accurate, authentic and complete data that reflects the actual experience of the patient in the study, i.e. source data verification. In addition, monitoring must ensure that the safety and rights of subjects are being protected. The investigator must ensure that the hospital notes will be available for direct verification of source data. The sponsor will not keep any records of patient's full identity.

To this end, the investigator agrees to allow regular visits by the study monitors and ensures direct access to study documents. He/she also agrees to allocate their time and the time of their staff to discuss findings and any issues with the monitor.

Medical monitors and CRAs or assistants may request to witness patient evaluations occurring as part of this protocol. The investigator and appropriate personnel will be periodically requested to attend meetings or trainings organised by the sponsor to ensure acceptable protocol execution.

The study may be audited or inspected by the sponsor (or a designated CRO), regulatory or health authorities or IEC/IRB. If such an audit or inspection occurs, the investigator must agree to allow access to the study site, required patient records and study documents. If notified of audits/inspections by bodies other than the sponsor, the investigator is to notify the sponsor of any such inspection immediately. By signing this protocol, the investigator grants permission to personnel from the sponsor, its representatives, and appropriate regulatory authorities for on-site monitoring of all appropriate study documentation, as well as on-site review of the procedures employed in the CRF generation, where clinically appropriate. The investigator agrees to allocate his/her time and the time of the study team to accompany the audit and to discuss the findings with the auditor. The investigator will be informed about the outcome of the audit.

The following activities will be undertaken to ensure the quality of trial-related activities:

- Adherence to the trial site SOPs to maintain accurate and consistent practices and procedures
- Conduct of a site initiation visit to ensure the investigator and all personnel involved in the trial understand the protocol, including the study procedures and their responsibilities
- Completion of a standard CRF in accordance with GCP requirements to ensure accurate and reliable data
- Periodic monitoring to ensure the trial data are accurate, complete and verifiable from source documents, and that the protocol is being followed

Quality control procedures regarding data entry and statistical analysis will be documented in the SAP.

### **10.3 Data Processing**

The CRO will be responsible for the processing and quality control of data. Data management will be carried out as described in the CRO's SOPs for clinical studies to ensure the integrity of the data, e.g. removing errors and inconsistencies of the data. Data entry and correction will be tracked by a validated audit trail. All systems are validated and compliant to FDA's ordinance 21 CFR part 11.

The FDA-validated medical dictionary MedDRA (current version) will be used for data coding (e.g. AEs, baseline findings, medication, medical/surgical history). The processes used for coding will be specified in the SAP.

### **10.4 Data Confidentiality**

#### **10.4.1 Documentation of Patients' Participation**

For all patients who give informed consent, regardless of whether they receive any study medication, the investigator must record patient identification data in the "Patient Identification List" (full name, initials, date of birth, patient identification code). The patient identification list must allow for the definite identification of any patient that takes part in the study. In addition, study participation must be documented in the patient's regular medical records. For details about patient identification, see Section [4.5](#).

#### **10.4.2 Data Protection**

To protect the patient's identity, a unique patient identification code will be assigned by the investigator to each trial patient and used in lieu of the patient's name when the investigator reports adverse events and/or other trial related data (see Section [4.5](#)). Thus, this number, rather than the patient's name, will appear on all documents and will be cross-referenced by the patient's date of birth. Personal information will be treated as confidential, but may need to be reviewed by the PIs, the ethics committee and regulatory authorities.

In order to be compliant with any country-specific laws, all relevant submissions to the respective authorities will be done and the corresponding approvals will be obtained before collection of any data considered to be sensitive, such as: ethnic origin, race, full date of birth etc.

### **10.5 Auditing**

A member of the sponsor's (or a designated clinical research organisation, e.g. a CRO) quality assurance unit may arrange to visit the investigator in order to audit the performance of the study at

the study site and the study documents originating there. The auditor(s) will usually be accompanied by a CRA or the study team lead. The investigator will be informed about the outcome of the audit.

In addition, inspections by health authority representatives – including foreign authorities – and IEC(s) / IRB(s) are possible at any time. The investigator is to notify the sponsor of any such inspection immediately.

## **10.6 Archiving**

The sponsor and the investigator / medical institution shall, in every case, retain the essential documents relating to this study for at least 25 years after its completion. They shall retain the documents for a longer period if required by other applicable regulatory requirements or by a separate agreement between the sponsor and the investigator. Essential documents shall be archived in such a way that ensures that they are readily available upon authorities' request.

Electronic CRFs (including queries and audit trails) will be retained by the sponsor, and copies will be sent to the investigator to maintain as the investigator copy.

Patient (hospital) files will be archived according to local regulations and in accordance with the maximum period of time permitted by the hospital, institution or private practice. The ISF is not to be destroyed without the sponsor's approval. The investigator's contract will contain all regulations relevant for the study centre.

Storage is described in Section [10.1.3](#).

## **11 Premature Termination of the Study**

At the discretion of the PI, the patients' treatment may be interrupted for medical reasons. In addition, the sponsor retains the right to end the study for medical-scientific or GCP-relevant reasons. In case of premature termination, the investigators, IRB / IECs and regulatory authorities will be informed by the study manager. As required by local law, current safety-relevant information will be provided to the IEC / IRB and the regulatory authorities by the sponsor. The sponsor will also inform all investigators about relevant safety events according to the applicable regulations. Stopping criteria are described in Section [11.1](#).

If the trial is prematurely terminated or suspended for any reason, the investigator should promptly inform the trial subjects and should assure appropriate therapy and follow-up. Should the study be terminated and/or the site closed for whatever reason, all documentation will be stored at the institution for the legally required period. Access will be granted to the coordinating CRO during this period. All study medication pertaining to the study must be returned to the sponsor or its representative in compliance with the applicable local regulations.

## 11.1 Stopping Criteria

### 11.1.1 Stopping Criteria for the Entire Trial

The entire study must be stopped if there is evidence of serious safety issues. An independent data safety monitoring board (IDSMB, see Section 11.2) will review safety data at regular intervals and may suggest terminating the trial.

To identify any possible safety issues in due time, all SAEs, deaths, instances of DMT (see Section 5.4.3.2), any instances of premature treatment discontinuation, as well as other AEs of interest (e.g. creatinine values) will be reviewed by the IDSMB on an ongoing basis during treatment of the first 36 PRRT patients who have actually received a  $^{177}\text{Lu}$ -edotreotide dose. Written safety assessments with conclusions and recommendations will be initially issued by the IDSMB for every 12 PRRT patients (i.e. after patient 1 - 12, 13 - 24, and 25 - 36), thereafter in 6-monthly intervals (see Section 11.2). The IDSMB will take into consideration the observed safety data, the safety profile of comparable PRRT agents, the safety profile of other licensed treatments for neuroendocrine tumours, and the natural history of the disease when making a recommendation to stop the trial.

The IDSMB may recommend to stop the trial for any serious safety issue of concern.

Only patients who have actually received at least one PRRT cycle will be considered for these stopping criteria.

Statistical stopping criteria are not planned.

The study may also be stopped by the sponsor for medical-scientific or GCP-relevant reasons.

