### 1.3 Benefit-Risk Assessment

The prognosis of GEP-NET patients is poor in most cases, since the disease is typically diagnosed at a late stage once the tumour has become non-resectable and/or has metastasised already (Modlin et al., 2008). For patients with metastasised P-NET (mP-NET), the observed 5-year survival rates are the lowest reported and vary between 25%-60% (Öberg et al., 2012), 27-43% (Ramage et al., 2012) and 38% (Lawrence 2011), in spite of using all available treatment options, including surgery,

symptom control with SSA and/or chemotherapy. Everolimus (Afinitor®) and sunitinib (Sutent®) are two drugs currently licensed for treatment of P-NET in the EU and USA, based on a median PFS (vs. placebo) of 11.0 (vs. 4.6) (Yao et al., 2011) and 10.2 (vs. 5.4) (Blumenthal et al., 2012) months, respectively. Lanreotide (Somatuline®) has also been approved by the FDA for GEP-NET. Study results showed a median PFS of 18.0 months for placebo (Caplin et al., 2014) and recently a corrected median PFS of 30.8 months for lanreotide (Caplin et al., 2016), but none of the enrolled patients in this study was in progression. Most recently, everolimus (Afinitor®) was also licensed both in the USA and the EU for treatment of non-functional GE-NET and lung NET based on a median PFS of 11.0 months vs. 3.9 months in placebo (Yao et al., 2016).

Well-documented evidence of clinical safety and efficacy of Lu-edotreotide in patients with mNET is available from the academic study, mentioned above (van Echteld et al. 2015, Baum et al., 2016). Fifty-six (56) patients (27 female, 29 male, mean age 64.4 years) presenting with progressive NET disease, were administered 1 to 4 doses of Lu-edotreotide PRRT as sole treatment option until a new diagnosis of disease progression.

For patients with metastasised GEP-NET, who received  $\geq 2$  Lu-edotreotide cycles, a median PFS of 34.5 months was reported (van Echteld et al. 2015, Baum et al., 2016). It is, therefore assumed, that patients assigned to Lu-edotreotide treatment may experience a significant individual benefit, compared to those assigned to standard treatment.

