## **11.2 Independent Data Safety Monitoring Board**

An independent data safety monitoring board (IDSMB) will review safety data at regular intervals throughout the study. If there are any signs of safety issues, the IDSMB may suggest terminating the trial.

Corresponding to the previously described toxicity pattern for PRRT agents (IAEA PRRT monograph 2013), the IDSMB will put special emphasis on identifying possible acute and delayed radiotoxic effects which are predominantly expected for bone marrow and kidneys.

To identify relevant safety issues in a timely fashion, the IDSMB will perform an ongoing review of SAE notifications, deaths, instances of DMT (see Section 5.4.3.2), instances of patients not meeting the pre-defined eligibility criteria for continued administration of Lu-edotreotide after cycle 1 (see Section 5.4.1.2), or other toxicities requiring discontinuation of Lu-edotreotide treatment in the opinion of the investigator, as well as other AEs of interest (e.g. creatinine values). The IDSMB will prepare summary reports with safety assessments and recommendations. For the first 36 PRRT patients, the IDSMB will review 3 consecutive cohorts of 12 PRRT patients who have reached the day 90 (±14) day evaluation (i.e. baseline for cycle 2), allowing to characterise a representative safety profile at the end of this treatment cycle, but will also consider any available additional data from patients who have already advanced beyond cycle 1 at the time of review. After the first 36 PRRT patients, the IDSMB will convene in 6-monthly intervals. Details will be described in the IDSMB charter.

Results of previous trials have shown that Lu-edotreotide has the potential to perform considerably better than current standard therapy (Baum et al., 2016). Therefore, termination for futility was not considered. Patients who experience progression under everolimus may switch to treatment with Lu-edotreotide off-study at the discretion of the Investigator (see Section 7.4.2).

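### The whole-trial safety stopping criteria count only PRRT-treated patients and require no comparison with the concurrent everolimus arm, so attribution of excess deaths or SAEs rests on outside references

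*Protocol*

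**What the plan says.** Protocol 11.1.1 requires the study to stop if there is evidence of serious safety issues and gives the IDSMB the task of looking for it. Four statements in that section matter here.

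- Who counts: "Only patients who have actually received at least one PRRT cycle will be considered for these stopping criteria".
- What the board weighs: the observed safety data, then "the safety profile of comparable PRRT agents, the safety profile of other licensed treatments for neuroendocrine tumours, and the natural history of the disease".
- Form of the criteria: "Statistical stopping criteria are not planned".
- Discretion: "The IDSMB may recommend to stop the trial for any serious safety issue of concern".

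Reports are due after each of the first three groups of 12 PRRT patients, then every six months.

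Protocol 11.2 is broader in one respect and equally PRRT-centred in another. It opens without limiting the review to one arm: "An independent data safety monitoring board (IDSMB) will review safety data at regular intervals throughout the study". It lists SAE notifications and deaths, again with no arm named. Its treatment-specific items all concern PRRT: dose-modifying toxicity under 5.4.3.2 (not the everolimus counterpart, 5.4.3.1), failure to qualify for further cycles, and discontinuation of the radiopharmaceutical. For the early phase, "the IDSMB will review 3 consecutive cohorts of 12 PRRT patients who have reached the day 90" evaluation. Further detail is left to the IDSMB charter, which is not among the documents.

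Neither the protocol nor the SAP specifies a between-arm safety comparison for the stopping decision.

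**The concern.** The trial has a concurrent randomised control, the natural yardstick for deciding whether deaths or SAEs exceed what the disease produces. Section 11.1.1 sets it aside by an explicit rule; this is not merely a missing detail.

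Attribution is hard in this trial for three reasons.

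- Under Protocol 8.3.2.6, deaths and other serious events linked to progression are SAEs, so the PRRT event stream mixes drug and disease.
- Causality is judged by open-label investigators. The same section treats an SAE of unassessable relationship as unlikely to be related, pending follow-up. Event rates by arm do not depend on those judgements.
- The toxicities overlap. Protocol 1.3 lists anaemia for everolimus, and Appendix 4 covers thrombocytopenia and neutropenia.

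If the outside reference is wrong for this population, the board may raise an alarm over disease events or accept a true excess as normal. Patients randomised to PRRT who die before their first dose, planned within 21 days of randomisation (Protocol 5.2), also fall outside the criteria.

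**Working it through.** Section 11.1.1 states no threshold, rate, alpha or power, so there is no plan figure to reproduce. The figures below are illustrations. The documents give no SAE rates, so all event rates are assumptions except those derived from the survival figures in Protocol 1.3 and SAP section 4.

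**1. Spread of the outside yardstick.** Protocol 1.3 gives three 5-year survival figures (S5) for metastasised P-NET: 25–60%, 27–43% and 38%. With a constant hazard, 12-month mortality is 1 − S5^(1/5).

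| 5-year survival | 12-month mortality |
|---|---|
| 25% to 60% | 24.2% to 9.7% |
| 27% to 43% | 23.0% to 15.5% |
| 38% | 17.6% |

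The 44-month median OS in SAP section 4 gives 1 − 0.5^(12/44) = 17.2%. The answer depends on which source is chosen, and all three ranges cover P-NET only.

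**2. Effect of a wrong benchmark.** Take 36 PRRT patients and a hypothetical flag at the smallest count whose one-sided exact binomial tail is at most 5%.

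| Benchmark rate | Flag at | Tail at benchmark | Chance of flag if background is 10 points higher, no drug effect |
|---|---|---|---|
| 10% | ≥8 | 2.4% | 43% |
| 20% | ≥12 | 4.2% | 39% |
| 30% | ≥16 | 4.7% | 35% |

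The opposite error also occurs. If the true background is 10%, PRRT doubles it to 20% and the benchmark is 20%, the flag fires only 4.2% of the time.

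**3. What a concurrent comparison adds.** Randomisation is 2:1 (Protocol 5.2), so 36 PRRT patients come with about 18 on everolimus. Power is at two-sided 5%: exact Fisher at 36 vs 18, normal approximation with pooled null variance at 200 vs 100.

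| Everolimus vs PRRT rate | 36 vs 18 | 200 vs 100 |
|---|---|---|
| 10% vs 20% | 9% | 60% |
| 20% vs 40% | 25% | 95% |
| 30% vs 50% | 25% | 92% |

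For 10% vs 20% at 200 vs 100:

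- Pooled rate = (40 + 10)/300 = 0.1667
- Null SE = √(0.1667 × 0.8333 × (1/200 + 1/100)) = 0.0456
- Alternative SE = √(0.16/200 + 0.09/100) = 0.0412
- Power = Φ((0.10 − 1.96 × 0.0456)/0.0412) = Φ(0.26) ≈ 60%

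An unpooled variance gives Φ(0.10/0.0412 − 1.96) ≈ 68%; the pooled figure is the one to use.

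**4. Deaths.** At a 44-month median, 3-month mortality is 1 − 0.5^(3/44) = 4.6%. That is 1.7 expected deaths in 36 patients and 0.8 in 18. At 12 months with 200 vs 100 and a control rate of 17.2%, power is 30% for a hazard ratio of 1.5 (24.7% on PRRT) and 77% for 2 (31.5%).

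**The case against.** The strongest reply is that 11.1.1 describes expert judgement and contains no counting rule. With no statistical criteria, there is no tally from which everolimus patients are dropped. The board may act on any serious safety issue, its review in 11.2 carries no arm restriction, and the charter may already call for tables by arm. The observed safety data come first among the things to weigh, and other licensed treatments include everolimus as a class. The PRRT focus has a stated reason: 11.2 emphasises marrow and kidney radiotoxicity, whereas everolimus is licensed standard treatment. The restrictive sentence may partly be meant to leave out patients assigned to PRRT but never dosed.

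Much of this stands. A reader might infer that everolimus data are missing from every board report, that serious harm on everolimus could never lead to a stop, or that drug effects cannot be separated from disease. The documents support none of these: the sentence limits the criteria, not what the board sees, and the charter is unseen.

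Three practical objections also stand.

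- The arms do not supply identical data. PRRT patients have extra haematology at weeks 2, 4, 6 and 8 after each dose (Table 1, footnote B) and extra chemistry at about 5 and 24 hours (7.3.1.1, 7.3.1.2). Rates per patient-year do not correct for more frequent testing.
- Sub-study C patients allocated directly to PRRT (3.6.3) are not randomised.
- At the first three reviews a concurrent comparison adds little.

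What does not stand is that 11.2 repairs 11.1.1. A general duty to review safety data does not override an explicit restriction, and an unseen charter cannot be assumed to do so.

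**Conclusion.** The point holds as a stated restriction that should be changed. Section 11.1.1 confines the whole-trial stopping criteria to PRRT-treated patients, requires no comparison with the randomised everolimus arm, and sits uneasily with its own discretion clause and with 11.2. Attribution of an excess of deaths or SAEs therefore rests, as written, on outside references.

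The benefit of the change falls mainly at the later 6-monthly reviews. The 60% figure assumes rates of 10% and 20%, all 300 patients followed for the event, and a single test. It measures information and does not propose a boundary. The mortality conversions assume a constant hazard, and the P-NET survival figures do not describe the whole GEP-NET population.

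**What to change.** Replace the restrictive sentence in 11.1.1 with wording to this effect:

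> The board considers safety data from both arms: deaths in all randomised patients, and other safety data in all patients who received either study treatment.

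Then align 11.1.1, 11.2 and the charter as follows.

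- Closed reports show deaths, SAEs, grade 3 or higher haematology and creatinine/eGFR by arm, as counts and per patient-year.
- Laboratory comparisons use visits common to both arms; the extra PRRT samples are reported separately.
- Sub-study C patients allocated directly to PRRT are shown apart from the randomised comparison.
- The 12-patient PRRT cohort reviews and the PRRT-specific lists stay as they are.

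The cost is protocol and charter wording plus a small amount of extra reporting. The data are already collected in both arms, and SAP 8.1 and 8.4 already tabulate adverse events and laboratory results by arm.

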### 11.1.2 Stopping Criteria for Individual Patients

Study participation for an individual patient *must* be stopped

- In case of tumour progression (see Section 8.2.4)
- In case of excessive toxicity defined as an AE considered by the Investigator to necessitate permanent discontinuation of  $^{177}\text{Lu}$ -edotreotide, e.g., serious, treatment-related adverse events (see Section 8.3.2.5)
- If the patient decides to withdraw from the trial (see Section 13.2)

Study participation for an individual patient *may* be discontinued (see Section 4.4.1):

- For medical reasons at the discretion of the Investigator
- Due to non-compliance
- Following a protocol deviation
- Due to pregnancy
- If the patient is lost to follow-up.

Study treatment for an individual patient *must* be discontinued in the case of pregnancy (see Section 4.4.1). See Section 8.3.1.1 for follow-up procedures in the case of pregnancy.

Lu-edotreotide treatment for an individual patient *must* be discontinued in the case of hypersensitivity or anaphylactic reaction, or TLS or CRS development (see Section 8.3.2.4).

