### 4.4 Withdrawal of Patients from Study Participation or Medication

#### 4.4.1 Withdrawal

Patients may decide to withdraw from the study at any time for any reason without prejudice to their further medical care. The investigator may withdraw a patient for any of the following reasons:

- Adverse event: if patient is unwilling to continue because of an AE or if continued participation of the patient would be an unnecessary risk to the patient's health, in the opinion of the investigator.
- Non-compliance
- Protocol deviation
- Pregnancy
- Lost to follow-up

A female patient who becomes pregnant during the treatment phase of the study must be discontinued from study treatment. See Section 8.3.1.1 for follow-up procedures in the case of pregnancy.

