## **4.7 Study Duration**

After providing informed consent, subjects will be screened for study enrolment, for up to 90 days prior to the first study treatment. Once enrolled and randomised to treatment, subjects will stay in the study until disease progression is established per RECIST 1.1 criteria, an alternative treatment for GEP-NET is initiated, the subject is withdrawn from the study, or for 30 months, whichever occurs first.

A subject randomised to everolimus (Afinitor®) who has disease progression must end study participation but may be offered Lu-edotreotide therapy based on the personal judgement of the Investigator, if he/she considers it appropriate and likely to be beneficial for the individual patient (see Section 7.4.2).

The maximum duration of participation for individual subjects is 30 months. The observation time for overall survival will be 5 years (60 months) after EOS for all patients (see Section 7.4).

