As only standard  $^{177}\text{Lu}$ -edotreotide doses of  $7.5 \text{ GBq} \pm 0.7 \text{ GBq}$  are used in this study, dose modification will not be achieved by reducing the next planned dose, but by delaying the next treatment cycle up to a maximum of 4 weeks (week 16 (+ 2)). In such a situation, subsequent PRRT cycles and evaluations (except for evaluation of tumour response based on morphological imaging RECIST 1.1) will be performed in intervals of 90 ( $\pm 14$ ) days, calculated from the delayed PRRT cycle. In case toxicity has not recovered by week 16, a patient cannot receive further PRRT cycles, but will remain in the study.

Following the second occurrence of DMT, the patient is excluded from further treatment, but will remain in the study.

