### **8.3.2.3 Assessments and Documentation of Adverse Events**

All adverse events which occur up to EOS, both those observed by study site personnel and those spontaneously reported by study patients, must be recorded on the ‘adverse event’ page(s) in the

CRF regardless of causality. AEs ongoing at EOS have to be followed up until resolved or for a period up to a maximum of 30 days by the investigator.

If an adverse event fulfils any of the criteria for a SAE, both the adverse event pages of the CRF and the Serious Adverse Event Form must be completed. SAEs are recorded for the entire duration of the study. For details of how to report SAEs see Section [8.3.2.5](#).

For both Serious and Non-serious AEs, documentation must be supported by an entry in the patient's hospital notes. Required information includes: the type of adverse event, seriousness of the event, start date, date of resolution, actions required, outcome, and an assessment of its relationship to study drug and an estimate of its severity (using NCI-CTCAE, version 4.03). NCI-CTCAE severity will be marked in the SAE Report Form using the numeric grades: grade 1 (mild), grade 2 (moderate), grade 3 (severe), grade 4 (life-threatening) and grade 5 (fatal).

All abnormal laboratory results, which are considered to be clinically relevant by the investigator, should also be recorded as adverse events. If an abnormal laboratory result meets any of the criteria for a SAE, this must also be reported on a Serious Adverse Event Form.

An AE should be documented with the applicable diagnosis, if possible (rather than as a symptom, sign, or laboratory finding).

All adverse events that meet the criteria for serious require the completion of a SAE Report Form, in addition to being recorded on the AE pages of the patients' CRF. This applies to all SAEs, whether or not they were considered to be related to study treatment.

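### Protocol 11.1.2 ends study participation for an adverse event that permanently stops PRRT, while 5.4.3.2 keeps patients barred from PRRT for toxicity in the study; no precedence is set, so central PFS imaging may stop with the drug

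*Protocol*

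**What the plan says.** Protocol 11.1.2 (Stopping Criteria for Individual Patients) gives a list of events after which participation *must* stop. One is: "In case of excessive toxicity defined as an AE considered by the Investigator to necessitate permanent discontinuation of" 177Lu-edotreotide, with serious treatment-related adverse events as the example. A separate list, under *may*, includes "For medical reasons at the discretion of the Investigator". A further sentence says that 177Lu-edotreotide treatment must "be discontinued in the case of hypersensitivity or anaphylactic reaction, or TLS or CRS development"; it does not mention participation.

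Protocol 5.4.3.2 deals with DMT under PRRT. If toxicity has not recovered by week 16, "a patient cannot receive further PRRT cycles, but will remain in the study". For a repeat: "Following the second occurrence of DMT, the patient is excluded from further treatment, but will remain in the study".

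Protocol 4.4.1 makes withdrawal for an adverse event optional in both arms: "The investigator may withdraw a patient for any of the following reasons". Protocol 4.7 says that "subjects will stay in the study until disease progression is established per RECIST 1.1 criteria, an alternative treatment for GEP-NET is initiated", and the same sentence goes on to list withdrawal from the study and month 30.

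On the endpoint, Protocol 4.6 makes withdrawal the patient's end of study, and 8.2.1.2 runs 3-monthly MRI/CT until progression or end of study. Protocol 9.2.1 and SAP 3.4.1 censor withdrawals in the primary PFS analysis, which uses blinded central reads.

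**The concern.** A patient who stops PRRT for toxicity can be handled in two ways. Under 5.4.3.2 the patient keeps the scheduled scans and can still contribute a centrally read PFS event. Under 11.1.2 the patient leaves, the scheduled scans end, and PFS is censored at the last adequate assessment unless there is a central progression or a qualifying death.

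Sites reading different sections would follow the same event differently. Stopping for toxicity may also be related to later progression, so this censoring need not be independent of outcome. The mandatory rule names only 177Lu-edotreotide. For everolimus, Appendix 4 discontinues treatment only, and leaving the study is discretionary. The loss of follow-up could therefore differ between arms in the primary comparison.

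**Working it through.** **1. The rules side by side**

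| Place | Trigger | Consequence |
|---|---|---|
| 11.1.2, *must* list | AE judged by the investigator to need permanent stop of PRRT | Participation ends |
| 5.4.3.2 | DMT unresolved at week 16, or second DMT | PRRT ends, patient stays |
| 4.4.1; 11.1.2 *may* list | AE or medical reason, either arm | Participation may end |
| 11.1.2, last sentence | Hypersensitivity or anaphylaxis, TLS, CRS | PRRT ends; silent on participation |

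**2. Overlap.** The DMT list includes any other Grade 4 toxicity at least possibly related to study drug, apart from liver enzymes. The example in 11.1.2 is serious, treatment-related events. One patient can meet both. Laboratory DMT can also be an adverse event, since 8.3.2.3 says: "All abnormal laboratory results, which are considered to be clinically relevant by the investigator, should also be recorded as adverse events". Neither section refers to the other on this point. Section 4.7 does not settle it: withdrawal from the study is on its list, so it fits either reading.

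**3. What an exit does to the data.** The early withdrawal visit seeks the EOS evaluations, MRI/CT included, within 28 days. The minimum list in 7.3.11, used when that visit cannot be completed, has no MRI/CT. Afterwards 7.4.1 provides 6-monthly contacts on survival and progression status, which SAP 3.1 describes as local progression data.

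**4. Base case for scale.** The documents give no figure for this issue. SAP section 4 uses medians of 17 and 11 months, so HR = 11/17 = 0.6471, with 180 events (112 and 68). Power from that split: |ln 0.6471| / √(1/68 + 1/112) − 1.96 = 0.87, or 80.8%, which agrees with the stated 80%. Expected events by month 30 under exponential PFS without drop-out, n × (1 − exp(−ln 2 × 30/median)):
- everolimus: 100 × (1 − exp(−1.890)) = 84.9
- PRRT: 200 × (1 − exp(−1.223)) = 141.1
- total: 226.0

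**5. Effect on the hazard ratio, by simulation.** From the SAP: 200 vs 100 patients, the medians above, a 30-month limit and 15% drop-out. Assumed, because the documents give nothing: exit shares, exit times (PRRT month 3, 6 or 9; everolimus months 1 to 12) and the factor by which the hazard changes after exit. Shift = HR with imaging continued − HR with censoring at exit, so plus means that censoring favours PRRT. The two shift columns count the exit percentage differently: as a share of each arm, where patients who progress first never exit, or as a share of patients still progression-free.

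| Exits PRRT/everolimus | Later hazard, both arms | Shift, share of arm | Shift, share of progression-free |
|---|---|---|---|
| 10%/0% | ×1 | 0 (0.644, 0.644) | within 0.002 of 0 |
| 10%/0% | ×2 | +0.03 (0.675, 0.645) | +0.040 (0.684, 0.644) |
| 15%/0% | ×2 | +0.045 | +0.060 |
| 5%/15% | ×2 | −0.02 | −0.036 |
| 10%/10% | ×2 | about 0 | +0.001 |

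Between the two counts, the range for 5%/15% to 15%/0% is about −0.03 to +0.05. On the second count, if half of those leaving start new anticancer therapy (censored either way under SAP Table 1), the ends shrink to −0.021 and +0.032. With 10%/10% exits but an unequal hazard change, the shift is +0.040 if only the PRRT hazard doubles and −0.038 if only the everolimus hazard doubles.

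**6. Effect on events.** At 15%/15% of each arm and ×2, mean events fall from 220 to about 192, and 93% of trials still reach 180. If the exits are taken as part of the SAP's 15% drop-out allowance, about 204 events remain and over 99% of trials reach 180.

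**The case against.** The two sections can be read together. The DMT rule is specific and threshold-based and tells the site to keep the patient; 11.1.2 is a general rule for excessive toxicity. On that reading the true overlap is a DMT that the investigator also regards as excessive. This narrows the problem but does not remove it: 11.1.2 has no carve-out for DMT, and its non-DMT cases still leave imaging when the drug stops.

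The contrast between arms is less sharp than mandatory against discretionary suggests. The PRRT exit also rests on investigator judgement, and it arises mainly while cycles are being given, about nine months. That stands.

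There are safeguards. SAP 3.4.1 lists possible sensitivity analyses on drop-out pattern and on local reads, and SAP 6.6 tabulates DMTs and treatment discontinuations with reasons in each arm. These would show the extent of the problem. They cannot supply central scans that were never taken.

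Nothing in the documents shows that the hazard rises after PRRT stops. Protocol 1.3 points the other way for PRRT: 34 of 37 responders first responded after cycle 1, and benefit may develop months after the last cycle. Everolimus is described as acting by continuous inhibition. That would move the shift against PRRT, through exits that 11.1.2 does not force. This stands, and is why no direction is claimed.

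Two stronger textual readings are tempting. A reader might infer that 11.1.2 contradicts itself on hypersensitivity, TLS and CRS. It requires treatment to stop and says nothing about participation, so both instructions can be obeyed; it is unclear, not contradictory. A reader might also infer that 4.7 conflicts with 11.1.2. It does not, because it lists withdrawal from the study.

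**Conclusion.** The conflict is real and should be corrected. Two sections give different instructions for overlapping toxicity stops, nothing sets precedence, and the choice decides whether the patient stays under central imaging for the primary endpoint.

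The consequence is possible bias of unknown direction and size. There is none if the hazard after exit is unchanged, and about none if it changes equally in both arms with similar exit shares. With a doubled later hazard in both arms, the HR shift is about −0.03 to +0.05 for exits of 5%/15% to 15%/0% (PRRT/everolimus). Exit shares, timing and later hazard are all assumed.

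A reader might infer that the rule favours PRRT. That needs more PRRT than everolimus exits, or a larger hazard rise after PRRT, and the documents support neither. A reader might also infer that the trial would run short of events. The least favourable count (15%/15% of progression-free patients, ×2, on top of the full 15% drop-out) gives 184 events with 71% of trials reaching 180, but it adds toxicity exits to an allowance that may already include them. On the counts in step 6, 180 events remain likely, and SAP Table 3 also allows the final analysis once all patients reach EOS.

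**What to change.** Amend the toxicity bullet in Protocol 11.1.2 so that an adverse event requiring permanent discontinuation of 177Lu-edotreotide ends study treatment, not study participation, in line with 5.4.3.2. Add one sentence for both arms: after study drug stops for toxicity, the scheduled 3-monthly MRI/CT with central read continues until progression, new anticancer therapy, death, withdrawal of consent or month 30.

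The cost is two protocol edits, using scans already in the schedule. Some patients off study drug may decline visits, so some censoring will remain. No SAP change is needed.
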